4.2.13 Safety data

Safety and tolerability data from all cycles of treatment will be combined and will be presented by treatment group using the safety population. Safety summaries will be descriptive only. No formal statistical analyses will be performed on the safety data.

The following sections describe the planned safety summaries for AEs, laboratory parameters, vital signs, ECG and WHO/ECOG performance status. However, additional safety summaries (not specified in this SAP) may need to be produced to aid interpretation of the safety data.

4.2.13.1 Adverse events

All AEs, both in terms of current MedDRA preferred term and CTCAE grade, will be summarized descriptively by count (n) and percentage (%) for each treatment group. The current MedDRA dictionary at the time of database lock will be used for coding wherever possible. The majority of the AE summaries, unless stated otherwise, will be based on TEAEs. Any AE occurring before study treatment (i.e. before the administration of the first dose on Study Day 1) will be included in the AE listings, but will not be included in the summary tables (unless otherwise stated). These will be referred to as 'pre-treatment'. However, any AE occurring before the administration of the first dose on Study Day 1 that is ongoing and increases in severity after the first dose will be regarded as treatment emergent and thus will be included in the majority of summary tables.

AEs observed up until 90 days following discontinuation of the study treatment or until the initiation of the first subsequent anti-cancer therapy following discontinuation of study treatment (whichever occurs first) will be used for reporting of all the AE summary tables. This will more accurately depict AEs attributable to study treatment only as some of AEs up

to 90 days following discontinuation of the study treatment are likely to be attributable to subsequent therapy.

However, to assess the longer-term toxicity profile, some of the AE summaries may also be produced containing AEs observed up until 90 days following discontinuation of the study treatment (i.e. without taking subsequent therapy into account).

All reported AEs will be listed along with the date of onset, date of resolution (if AE is resolved) and investigator's assessment of severity and relationship to study drug. Frequencies and percentages of patients reporting each preferred term will be presented (i.e. multiple events per patient will not be accounted for apart from on the episode level summaries which may be produced).

Summary information (the number and percent of patients by system organ class and preferred term separated by treatment group) will be tabulated for:

- All AEs
- All AEs possibly related to study medication (as determined by the reporting investigator)
- AEs with a maximum CTCAE grade 3 or 4
- AEs of any CTCAE grade 3 or 4
- AEs with a maximum CTCAE grade 3 or 4, possibly related to study medication (as determined by the reporting investigator) causality to be determined first, then max grade 3 or 4
- AEs with any CTCAE grade 3 or 4, possibly related to study medication (as determined by the reporting investigator) – causality to be determined first, then maximum grade 3 or 4
- AEs with outcome of death
- AEs with outcome of death possibly related to study medication (as determined by the reporting investigator)
- All SAEs
- All SAEs possibly related to study medication (as determined by the reporting investigator)
- AEs leading to discontinuation of study medication

- AEs leading to discontinuation of study medication, possibly related to study medication (as determined by the reporting investigator)
- AEs leading to hospitalization
- AEs leading to dose interruption of study medication
- Immune mediated AEs (as determined by the reporting investigator)
- Infusion reaction AEs (as determined by the reporting investigator)

An overall summary of the number and percentage of patients in each category will be presented. In addition, a truncated AE table of most common AEs and another table showing most common AEs with CTCAE grade 3 or 4 (maximum grade and any), showing all events that occur in at least 5% of patients overall will be summarized by preferred term, by decreasing frequency in the total column (the total column will not be displayed in the AE tables). This cut-off may be modified after review of the data. When applying a cut-off (i.e. x %), the raw percentage should be compared to the cut-off, no rounding should be applied first (i.e. an AE with frequency of 4.9% will not appear if a cut-off is 5%). Summary statistics showing the time to onset and the duration of the first AE may also be presented as appropriate.

Each AE event rate (per 100 patient years) will also be summarized by preferred term within each system organ class. For each preferred term, the event rate is defined as the number of patients with that AE divided by the total duration (days) summed over patients and then multiplied by 365.25 x 100 to present in terms of per 100 patient years.

Summaries of the number and percentage of patients with AEs will be provided by maximum reported CTCAE grade, system organ class, preferred term and treatment group.

Fluctuations observed in CTCAE grades during study will be listed for those AEs which are CTCAE \geq 3.

Deaths

A summary of all deaths will be provided with number and percentage of patients by treatment group in the FAS, categorized as:

- Total number of deaths (regardless of date of death)
- Death related to disease under investigation only as determined by the investigator.
- Death related to disease under investigation and an AE with outcome of death
 - AE onset prior to subsequent therapy, which includes AEs with an onset date (or pre-treatment AEs that increase in severity) on or after the date of first dose and up to and including 90 days following the last dose of study treatment, or

up to the date of initiation of the first subsequent therapy (whichever occurs first)

- AE onset after start of subsequent therapy, which includes AEs with onset date
 >90 days following the last dose of study treatment or AE start date ≥ the date of initiation of the first subsequent therapy (whichever occurs first)
- AE with outcome of death only
 - AE onset prior to subsequent therapy (as defined above)
 - AE onset after start of subsequent therapy (as defined above)
- Death after end of safety follow up period (last dose of study treatment + 90 days) and not due to AE or disease under investigation (*)
- Unknown reason for death
- Other deaths (deaths not captured in the earlier categories) e.g. death occurring after randomization but prior to receiving treatment and which is not related to disease under investigation

This summary will be produced twice; firstly, including all deaths and, secondly, including all deaths on-treatment or within 90 days of the last dose of study treatment. Hence the category marked (*) will only appear in the first summary.

Adverse events of special interest and possible interest

Preferred terms used to identify AESI and AEPI will be listed before DBL and documented in the Study Master File. Grouped summary tables of certain MedDRA preferred terms will be produced and may also show the individual preferred terms which constitute each AESI grouping. For each grouped term, the number (%) of patients experiencing any of the specified terms will be presented by maximum CTCAE grade. Time to onset of first AESI for each grouped term will also be produced. Groupings will be based on preferred terms provided by the medical team prior to DBL, and a listing of the preferred terms in each grouping will be provided.

Additional summaries of the above-mentioned grouped AE categories will include number (%) of patients who have:

- At least one AESI/AEPI presented by outcome
- At least one AESI/AEPI leading to discontinuation of study medication

A summary of total duration (days) of AESI/AEPI will be provided for events which have an end date, and these may be supported by summaries of ongoing AESIs at death and, separately, at DCO.

Additionally, there will be several summaries of AESIs/AEPIs requiring concomitant treatment, and particularly the relationship of AESIs/AEPIs to the use of immunosuppressive agents (i.e. depicting which AESI/AEPI triggered immunosuppressive use), endocrine treatment and systemic corticosteroids, and, separately, to the use of systemic corticosteroids at high doses.

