#### 8.3.2 Time period and frequency for collecting AE and SAE information

AEs and SAEs will be collected from the time of the patient signing the ICF until the follow-up period is completed (90 days after the last dose of IP). If an event that starts after the defined safety follow-up period noted above is considered to be due to a late-onset toxicity to study drug, then it should be reported as an AE or SAE as applicable.

All SAEs will be recorded and reported to the Sponsor or designee within 24 hours, as indicated in Section 8.4.1. The Investigator will submit any updated SAE data to the Sponsor within 24 hours of it being available.

Investigators are not obligated to actively seek AE or SAE in former study patients. However, if the Investigator learns of any SAE, including a death, at any time after a patient's last visit and he/she considers the event to be reasonably related to the study treatment or study participation, the Investigator should notify the Sponsor.

The method of recording, evaluating, and assessing causality of AE and SAE and the procedures for completing and transmitting SAE reports are provided in Appendix B.

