# 9.4.2 Calculation or derivation of safety variables

# 9.4.2.1 Adverse events

Data from all cycles of treatment will be combined in the presentation of safety data. "On treatment" will be defined as assessments between date of first dose of IP and 90 days following discontinuation of IP. For AEs, on treatment (or treatment-emergent AEs) will be defined as any AEs that started after first dose of IP or prior to dosing and which worsens following exposure to the treatment.

AEs observed up until 90 days following discontinuation of IP or until the initiation of the first subsequent therapy following discontinuation of treatment (whichever occurs first) will be used for the reporting of the AE summary tables. This will more accurately depict AEs attributable to study treatment only, as a number of AEs up to 90 days following discontinuation of IP are likely to be attributable to subsequent therapy. However, to assess the longer-term toxicity profile, AE summaries will also be produced containing AEs observed up until 90 days following discontinuation of IP (ie, without taking subsequent therapy into account). Any events in this period that occur after a patient has received further therapy for cancer (following discontinuation of IP) will be flagged in the data listings.

A separate data listing of AEs occurring more than 90 days after discontinuation of IP will be produced. These events will not be included in AE summaries.

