3.4.1 Adverse events (AEs)

AEs and SAEs will be collected throughout the study, from the date of informed consent until 90 days after the last dose of the study treatment. The Medical Dictionary for Regulatory Activities (MedDRA) (using the latest or current MedDRA version) will be used to code the AEs. AEs will be graded according to the National Cancer Institute Common Terminology Criteria for AEs (CTCAE Version 4.03). A treatment emergent adverse event (TEAE) is an AE with an onset date/time or a pre-existing AE worsening (taking the last grade prior to dosing as the reference) on or following the first dose of study treatment through to 90 days after the last dose of the study treatment or initiation of first subsequent therapy (whichever occurs first). All AEs will be listed however only TEAEs will be summarized. For each treatment group, in the unlikely event of the two components being administered separately then date of first dose/last dose will be considered as the earliest/latest dosing date of either component.

Adverse events that have missing causality (after data querying) will be assumed to be related to study drug ("durvalumab or placebo" or "tremelimumab or placebo"), with the exception of causality assessments that are not applicable for the patient, e.g. causal relation to durvalumab for patients in the placebo arm.

AEs of special interest (AESI) and AEs of potential interest (AEPI)

Some clinical concepts (including some selected individual preferred terms [PTs] and higher level terms [HLTs]) have been considered "AEs of special interest" (AESI) to the durvalumab program. AESIs represent pre-specified risks which are of importance to a clinical development program.

The AESIs reported in the AstraZeneca-sponsored durvalumab studies are defined as AEs with a likely inflammatory or immune-mediated pathophysiological basis resulting from the mechanism of action of durvalumab and requiring more frequent monitoring and/or interventions such as systemic corticosteroids, immunosuppressants, and/or endocrine therapy. Endocrine therapies include standard endocrine supplementation, as well as treatment of symptoms resulting from endocrine disorders (for example, therapies for hyperthyroidism include beta blockers [e.g. propranolol], calcium channel blockers [e.g. verapamil, diltiazem], methimazole, propylthiouracil, and sodium perchlorate).

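### The SAP makes the protocol's full 90-day AE summaries optional without declaring the change, and its deaths table puts fatal AEs starting after day 90 in a row labelled as following subsequent therapy

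*SAP*

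**What the plan says.** Protocol 9.4.2.1 sets the window for its main AE tables as 90 days after stopping study drug or the first subsequent therapy, "whichever occurs first) will be used for the reporting of the AE summary tables". It then adds a second set to show longer-term toxicity, ignoring subsequent therapy: "AE summaries will also be produced containing AEs observed up until 90 days following discontinuation of IP". For anything later it says "A separate data listing of AEs occurring more than 90 days after discontinuation of IP will be produced", and it keeps those events out of the AE summaries.

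SAP 4.2.13.1 uses the same main window: "whichever occurs first) will be used for reporting of all the AE summary tables". On the second set it says "some of the AE summaries may also be produced containing AEs observed up until 90 days following discontinuation of the study treatment".

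SAP 3.4.1 ends the treatment-emergent (TEAE) window at 90 days after the last dose or at first subsequent therapy, if earlier, and states: "All AEs will be listed however only TEAEs will be summarized".

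The deaths summary in SAP 4.2.13.1 divides fatal AEs into two rows by onset. The second row is headed "AE onset after start of subsequent therapy, which includes AEs with onset date" more than 90 days after the last dose, or on or after the start of subsequent therapy.

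**The concern.** The protocol explains why it wants both sets. The truncated tables isolate events attributable to study drug, and the full 90-day tables describe the longer-term profile. For a checkpoint inhibitor, whose immune-mediated effects may appear after dosing ends, the second set shows what happens after a patient moves to another therapy. Protocol 4.2.3 stops treatment at progression so that patients can take up another anticancer treatment, so an early cut is an expected part of the treatment pathway.

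If the second set is optional, the team can choose after seeing the data which of those tables exist. The reason given for truncation, that later events probably belong to the next therapy, is also weakest for events that the investigator has attributed to study drug. Yet the tables of possibly related AEs take the same cut.

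The deaths table matters for a different reason. It has no split by causality, so the row label is what a reader relies on. A label naming subsequent therapy points to another drug, and for some patients there was none.

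**Working it through.** No planned figure needs reproducing. The check is a comparison of texts, followed by one illustration on stated assumptions.

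**1. Main AE tables.** Protocol 9.4.2.1 and SAP 4.2.13.1 use the same cut. There is no discrepancy.

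**2. Full 90-day tables.** The protocol says they *will* be produced and sets no limit on which. The SAP says *some may* be. Both the commitment and the scope are weaker, and the SAP names no table that must exist in this form.

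**3. TEAE rule.** Suppose a patient starts new systemic therapy 35 days after the last dose and has an AE on day 40.
- Under the protocol, the on-treatment period runs to day 90 with no cut, and the TEAE definition has no end at subsequent therapy. The event belongs in the second set of summaries.
- Under SAP 3.4 and 3.4.1, both the on-treatment period and the TEAE window close at day 35. The event is not a TEAE, and 3.4.1 allows only TEAEs to be summarized.

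Read literally, 3.4.1 rules out even the optional tables in 4.2.13.1. That section is itself looser: it bases most summaries, not all, on TEAEs unless stated otherwise.

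**4. Declaration of changes.** SAP Section 6 has four entries: the assessor used for response rate, a PFS/OS labelling slip in the protocol's power statements, the added OS analysis, and the anti-drug antibody subsets. None concerns AE windows.

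**5. Deaths table.** Take a patient with no subsequent therapy and a fatal AE starting 100 days after the last dose.
- The first row requires onset no later than day 90. Since 100 > 90, the patient fails it.
- The second row accepts any onset after day 90. The patient is counted there, under a label about subsequent therapy.

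The same two rows appear twice: for deaths due to both disease and an AE, and for deaths due to an AE only.

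**6. Size, by assumption only.** If a share *f* of patients starts subsequent therapy at mean day *t* after the last dose, the part of the 90-day window removed is *f* × (1 − *t*/90).
- *f* = 20%, *t* = 60: 0.20 × (1 − 60/90) = 0.067, about 7%.
- *f* = 60%, *t* = 30: 0.60 × (1 − 30/90) = 0.40, or 40%.

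Both inputs are assumed. The result is observation time removed, not the share of AEs missed.

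**The case against.** Much of the AE handling is the protocol's own, and a reader could easily infer more than the documents support.

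- *The SAP introduced the cut at subsequent therapy.* It did not introduce it for the main tables. The protocol uses the same cut for the same reason. What the SAP changes is the status of the second set and the on-treatment and TEAE definitions.
- *The SAP wrongly leaves late drug-related AEs out of summaries.* Protocol 8.3.2 does collect an event after day 90 if it is "considered to be due to a late-onset toxicity to study drug, then it should be reported as an AE or SAE". But protocol 9.4.2.1 sends such events to a listing and excludes them from summaries. Collecting an event is not a promise to tabulate it, and a new table of related AEs at any time would conflict with that rule.
- *Late events disappear.* They do not. SAP 4.2.13.1 lists every AE with onset date and investigator causality, and late fatal AEs are counted in the deaths table.
- *Delayed immune toxicity is under-reported.* Exponential PFS with the planned medians gives 1 − 0.5^(24/10) = 81% of placebo and 1 − 0.5^(24/15.4) = 66% of durvalumab patients with an event by 24 months. These are PFS events, deaths included, not starts of new therapy. On this reasoning placebo would be cut more often, so the truncation need not flatter durvalumab.

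It can also be said that the deaths row is only loosely labelled, because its definition mentions the 90-day criterion and the table is produced twice: for all deaths, and for deaths up to 90 days after the last dose. Comparing the two versions does separate early deaths from late ones. It does not show which of the late ones followed another therapy, so that point stands.

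**Conclusion.** Two findings hold on the text. First, a firm protocol commitment to full 90-day AE summaries becomes optional and partial in the SAP. It is contradicted by the TEAE-only sentence in 3.4.1 and not declared in Section 6. The number of such tables the SAP guarantees is zero. Second, the deaths table misclassifies, by its own stated rule, any fatal AE starting after day 90 in a patient with no subsequent therapy.

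Neither finding rests on a numerical assumption. The consequence is a risk that toxicity after the start of new therapy is under-represented in the summary tables. Its size and its direction between arms cannot be established from the documents. The cut in the main tables and the listing-only handling of AEs after day 90 are the protocol's own rules and are not errors.

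**What to change.** 1. In SAP 4.2.13.1, state that the 90-day summaries regardless of subsequent therapy *will* be produced, at least for all AEs, Grade 3-4 AEs, SAEs, AESI/imAEs, AEs judged related to study drug, and fatal AEs. In SAP 3.4.1, amend the TEAE-only sentence so that it does not exclude these tables.
2. In the deaths table, in both places where the rows occur, split the second onset row into (a) fatal AEs starting on or after the first subsequent therapy and (b) fatal AEs starting more than 90 days after the last dose with no earlier subsequent therapy.

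The cost is SAP wording and a rerun of existing table programs with a second window flag. No new data are needed, since protocol 8.3.2 already collects AEs to 90 days after the last dose. The drawback is that the wider tables will include some AEs caused by subsequent therapy, so the truncated tables should remain beside them.

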Data presentations	23 July 2021, V2.0	Inclusion of text related to COVID-19 related summaries. Section 2.2, 4.2.22.	N/A	In line with AZ guidance for CSRs.
Data presentations	08 August 2022, V3.0	Section 3.3.1 (EORTC QLQ-C30 and QLQ-LC13). Update to categories of clinically meaningful changes.	N/A	To align with presentation in TFLs.
Data presentations	08 August 2022, V3.0	Section 4.1.2 (Visit window for safety and PRO assessments). Update to requirement for visit based tables and plots, to just require a minimum of 20 observations per treatment group.	N/A	Added to prevent very large tables or plots being produced that contain many cells with meaningless data.
Data presentations	08 August 2022, V3.0	Section 4.2.2 (PFS). Update to subgroup analyses for PFS to specify for the stratification factors, subgroups based on both the IVRS and eCRF data should be included (applicable for OS as well).	N/A	Added to allow for any discrepancies between the IVRS and eCRF data.

Data presentations	08 August 2022, V3.0	Section 4.2.9 (PFS2). Removal of 'Symptomatic progression in absence of objective radiological progression' as a PFS2 category.	N/A	This is not collected in the eCRF.
Data presentations	08 August 2022, V3.0	Section 4.2.11.1 (EORTC QLQ-C30 and QLQ-LC13). Additional summary for compliance tables to be presented for patients who have discontinued treatment.	N/A	To establish any differences in the compliance rates between the FAS and patients discontinuing treatment.
Data presentations	08 August 2022, V3.0	Section 4.2.13.1 (AEs). Additional summaries by AEs with max CTCAE grade 3 or 4.	N/A	Durvalumab program level update.
Data presentations	08 August 2022, V3.0	Section 4.2.13.1 (AEs). Further clarification provided on derivation of AEs with max/any CTCAE grade 3 or 4, possibly related to study medication.	N/A	Durvalumab program level update.
Data presentations	23 June 2022, V2.0	Section 4.2.19 Demographic and baseline characteristics data. Additional characteristics listed to correspond with outputs.	N/A	To be in line with data presented in TFLs.
Data presentations	20 March 2023, V4.0	To include additional plots for liver enzyme parameters, with outliers removed. Section 4.2.13.2.	N/A	To ensure plots are interpretable.
Other	23 July 2021, V2.0	Reference list updated. Section 7.	N/A	To include new references in line with SAP update.

Other	23 July 2021, V2.0	General minor formatting and text updates throughout.	Y (v4.0)	In line with CSP v4.0 update.

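### The table of related AEs of 'any' Grade 3 or 4 carries a maximum-grade rule, so as written it omits a related AE that goes from Grade 3/4 to Grade 5 on a later day

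*SAP*

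**What the plan says.** SAP section 4.2.13.1 lists the AE tables by system organ class and preferred term. For AEs of all causes it names two separate Grade 3/4 tables, one by maximum grade and one described as "AEs of any CTCAE grade 3 or 4". Neither has a derivation note.

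For AEs judged related by the investigator it again names two. The maximum-grade table has the note "causality to be determined first, then max grade 3 or 4". The next bullet is titled "AEs with any CTCAE grade 3 or 4, possibly related to study medication (as determined by the reporting investigator") and has the note "causality to be determined first, then maximum grade 3 or 4". Apart from the abbreviation, the two notes are the same.

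The same section asks for a table of "most common AEs with CTCAE grade 3 or 4 (maximum grade and any"), so the two versions are treated as different displays. On the counting unit it says: "Frequencies and percentages of patients reporting each preferred term will be presented". It also asks for an overall summary of patients in each category.

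Protocol section 8.3.4 collects, for each AE, the maximum grade and the changes in grade, keeping only the highest grade on any calendar day.

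**The concern.** The title of the second related table and its derivation note select different events. The title asks whether Grade 3 or 4 was ever recorded; the note asks whether the highest grade was 3 or 4. The two part company when an event passes through Grade 3 or 4 and ends at Grade 5.

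These are related toxicities that worsen to death. A reader who trusts the title would take the table, and the matching line of the overall summary, to include every patient who had a related Grade 3/4 event. Programmed from the note, it would not. Two programmers working from this bullet could also produce different tables.

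**Working it through.** The plan states no figure for this table, so there is nothing to reproduce. The check compares the two rules on recorded grade sequences.

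**Are 'any' and 'maximum' meant to differ?** Yes. The all-cause list has both, and the most-common-AE table asks for both. The SAP amendment history, used here only as evidence of intent, has the entry "Additional summaries by AEs with max CTCAE grade 3 or 4", which presents the maximum-grade tables as extra ones. It also has the entry "Further clarification provided on derivation of AEs with max/any CTCAE grade 3 or 4, possibly related to study medication", which names both versions. No other current text gives a different derivation for the related 'any' table.

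**One related AE, grades recorded on different days**

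| Grades | Title: some grade is 3 or 4 | Note: highest grade is 3 or 4 |
|---|---|---|
| 1 then 2 | out | out |
| 2 then 3 | in | in |
| 3 then 4 | in | in |
| 4 then 2 | in | in |
| 3 then 5 | in | **out** |
| 4 then 5 | in | **out** |
| 5 only | out | out |

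A rise to Grade 5 on the same calendar day is stored as Grade 5 only, so it meets neither rule.

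**Patients with more than one event.** The SAP does not say whether the maximum is per event, per preferred term or per patient. Seven constructed patterns show how the unit matters. They are not frequencies.

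- A: one AE, Grade 3
- B: one AE, Grade 3 then 5
- C: term X Grade 4, term Y Grade 5
- D: one AE, Grade 2
- E: term X Grade 3 then 5, term Y Grade 3
- F: Grades 3 and 5 on the same day, stored as 5
- G: term X Grade 3 then 5, and a second event of term X, Grade 3

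| Rule | Patients counted | Patient-term entries |
|---|---|---|
| Title | A, B, C, E, G = 5 | 1+1+1+2+1 = 6 (E has two terms) |
| Note, maximum per event | A, C, E, G = 4 | 4 |
| Note, maximum per term | A, C, E = 3 | 3 |
| Note, maximum per patient | A = 1 | 1 |

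B is lost under all three units. E stays in the overall line per event and per term, but only through term Y. G stays only per event.

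**Duplication.** If both related tables use the same unit, they are identical. If 'any' is per event and 'maximum' per patient, they differ on C, E and G, and B is still excluded from both.

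**Size of one patient.** With the planned arm sizes and all randomized patients treated, 1/262 = 0.38 percentage points for durvalumab or placebo, and 1/200 = 0.50 points for the combination arm.

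**The case against.** The best defence is that the note only fixes the order of steps, causality before grade, and that a sensible programmer would follow the title. That may happen, but the note is the only derivation given for this table, and it names the maximum.

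A second defence is that the two tables use different units: 'any' for patients with any related event whose own maximum is 3 or 4, and 'maximum' for the patient's highest grade. The SAP does not say so. The reading would make the tables differ, but it still leaves out a single event that goes from Grade 3/4 to 5.

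What stands is the point about scale. Most of the constructed patterns contain a Grade 5 event, so the counts say nothing about frequency here, and pattern C concerns two different events rather than one that worsens. The affected events also appear in the tables of fatal related AEs, related SAEs and all related AEs, in the summary by maximum grade, and in the listing of grade fluctuations for AEs of Grade 3 or higher. SAP section 4.2.13 makes safety summaries descriptive and allows further ones.

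**Conclusion.** The concern holds. The derivation note contradicts the table's title and, followed as written, leaves out any related AE recorded at Grade 3 or 4 and then at Grade 5 on a later day, whichever unit the maximum refers to. Whether a given patient also leaves the overall line depends on that unit and on the patient's other related events.

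The effect is confined to one descriptive table and its summary line. No hypothesis test, alpha level or stopping rule is touched, and no fatal event is lost from the report. The number of patients affected is not knowable from the documents. The conclusion assumes that the note is programmed literally and that grade changes are recorded as Protocol section 8.3.4 requires. Severity is low.

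**What to change.** In SAP section 4.2.13.1, change the note on the related 'any' bullet so that causality is determined first and then any Grade 3 or 4, including events that also reach Grade 5. Leave the note on the maximum-grade bullet as it is. A related AE at Grade 3 or 4 and later at Grade 5 then counts in the 'any' table and stays out of the 'maximum' table; an event recorded only at Grade 5 counts in neither, and all other sequences are unaffected.

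The cost is one phrase in the SAP and one program flag. No new data are needed.
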